3.0 Measures

3.1 Primary Measure

- CAPS-5 (Clinician-Administered PTSD Scale for DSM-5)

3.2 Secondary Outcome Measure

- Sheehan Disability Scale (SDS) for MPBC

3.3 Safety Measures

- Columbia Suicide Severity Rating Scale (C-SSRS)
- Adverse Events
- Treatment-emergent Adverse Events
- Serious Adverse Events
- Adverse Events of Special Interest
- Concomitant medication use
- Vitals signs during MDMA sessions

3.4 Exploratory Measures

- DSP-I (The Dissociative Subtype of PTSD Interview)
- ACE (Adverse Childhood Experience Questionnaire)
- BDI-II (Beck Depression Inventory II)
- CPGS (Chronic Pain Grade Scale)
- SCS (Self-Compassion Scale)
- AUDIT (Alcohol Use Disorders Identification Test)
- DUDIT (Drug Use Disorders Identification Test)
- MIES (Moral Injury Event Scale)
- PTGI (Posttraumatic Growth Inventory)
- BPAQ-SF (Buss Perry Aggression Questionnaire Short Form)
- AAQ-II (Acceptance and Action Questionnaire)
- WHOQOL-BREF (WHO Quality of Life-BREF)
- DRRI-II (Deployment Risk and Resilience Inventory-2)
- UFEC (Utilization of Facility-based and Emergent Care)
- OSU-TBI-ID (Ohio State University Traumatic Brain Injury Identification Method)

4.0 Study Design

This open-label, randomized Phase 2 study will assess the relative safety and effectiveness of two versus three Experimental Sessions of MDMA-assisted therapy in treatment-seeking veterans diagnosed with at least moderate PTSD.

The study was to be conducted in up to 60 participants, but the study was terminated early at approximately 20 participants. Randomization will occur in a 1:1 fashion. Randomization will be allocated to Group 1: 3 Experimental Sessions of MDMA-assisted therapy or Group 2: 2 Experimental Sessions of MDMA-assisted therapy.

For each participant, the study will consist of:

- **Screening Period:** Phone or in-person screen, informed consent, eligibility, and baseline assessments
- **Study Inclusion and Randomization:** Include eligible participants, randomize to group, complete baseline self-report measures,
- **Treatment Period:** 3 Preparatory Sessions, followed by 2 or 3 Experimental Sessions, depending on group. Each Experimental Session is followed by 3 Integrative Sessions.
- **Post treatment:** Clinical evaluation and self-report measures.
 - Note: the primary endpoint (T2) occurs approximately 1 month after the last experimental session. This means that the T2 occurs ~12 weeks after baseline for the 2-session group, and ~16 weeks after baseline for the 3-session group.
 - The 2-session group will have an additional clinical evaluation ~16 weeks post-baseline (T2.2).
- **Study Termination:** Clinical evaluation and self-report measures

A divided-dose of MDMA (120 mg initial dose, followed by a supplemental 40 mg dose), is administered during the Treatment Period with manualized therapy in two or three open-label monthly Experimental Sessions. This ~8-12-week Treatment Period includes three Preparatory Sessions prior to the first MDMA-assisted session. Each Experimental Session is followed by three Integrative Sessions of non-drug therapy. Experimental Sessions are followed by an overnight stay. The Primary Outcome measure, the change in CAPS-5 from Baseline, is assessed by a centralized IR pool at 7 weeks following the final treatment session (post treatment). The IR pool will be blinded to treatment arm assignment, visit number, and number of treatments received, and will not have access to data collected by the sites during the active Treatment Period. Self-reported PTSD symptoms will be assessed at the start of each treatment visit by the PCL-5.

Table 1: CAPS-5 Data Collection by Visit

CAPS Number	Visit	Description/Timing	Target Timing Post Baseline
Baseline CAPS-5 T1	Screening	Baseline 2-9 days after initial eligibility met	Not Applicable
CAPS-5 T2	V12 (2-session group) or V16 (3-session group)	Post Treatment Primary Outcome 28 to 35 days after last Experimental Session	~12 wk (± 7 days) or ~16 wk (± 7 days)
CAPS-5 T2.2	V13 (2-session group only)	Secondary outcome for 2-session group only 28 to 35 days weeks after T2	~16 wk (± 7 days)

Dose Selection

This study will compare the effects of two versus three open-label manualized Experimental Sessions of therapy assisted by set doses of MDMA HCl (referred to as MDMA throughout) as described in the table below, along with associated non-drug preparatory and integrative therapy. Similar MDMA doses to those proposed in this study have been safely used in previous Phase 2 and 3 studies sponsored by MAPS.

Table 2: Dose Regimen of MDMA

Experimental Session	Initial Dose	Supplemental Dose*	Min-Max Cumulative Dose
1	120 mg	40 mg	120 mg to 160 mg
2	120 mg	40 mg	120 mg to 160 mg
3	120 mg	40 mg	120 mg to 160 mg
Total Cumulative Dose: 2 Session Group		240 mg to 320 mg	
Total Cumulative Dose: 3 Session Group		360 mg to 480 mg	

* Unless initial dose is not tolerated or refused by participant

5.0 Randomization and Blinding

Participants will be randomized in 1:1 allocation to two versus three sessions of MDMA-assisted therapy.

To further minimize bias in measuring effectiveness, the sponsor will use an observer-blind, centralized, reliable IR pool to administer the Primary Outcome measure via live video interviews. The IR Pool will have no knowledge of AEs and will only evaluate participants at Baseline and at the assessments scheduled after each Experimental Session. The IR Pool is blinded to full study design, visit number, treatment assignment, number of treatments, and any data from the treating therapy pair after Baseline. IRs will be assigned to participants based on availability. Participants will be instructed to withhold study progress from IRs. Timing of CAPS-5 assessments are pre-specified in the study protocol within visit windows.

Sites will be required to make and document a specific number of attempts to obtain follow-up data per protocol. All randomized participants who receive at least one dose of IMP and complete at least one follow-up assessment will be included in the final *mitT* set.

6.0 Sample Size and Power Considerations

Due to the early termination of this study, the initial power estimates are no longer valid, and the primary efficacy analysis will not be executed.

7.0 Analyses

7.1 Analysis Sets

The following analysis sets are defined for this study:

- All Enrolled: all participants who sign informed consent and are initially enrolled
- Safety: all participants who receive any IMP

7.2 Missing Data Handling

Missing outcome data will not be imputed.

7.2.1 Partial or Missing Dates

The following conventions will be used to impute missing portions of dates for AEs and concomitant medications. Note that the imputed values outlined here may not always provide the most conservative date. In those circumstances, the imputed value may be replaced by a date that will lead to a more conservative analysis.

Start Dates:

1. If the year is unknown, then the date will not be imputed and will be assigned a missing value.
2. If the month is unknown, then:
 - a. The month and day of the first dose date will be imputed if the year matches the first dose date year.
 - b. Otherwise, 'January' will be assigned.
3. If the day is unknown, then:
 - a. The day of the first dose date will be imputed if the month and year match the first dose date month and year.
 - b. Otherwise, the first day of the month will be assigned.
4. In the event that an imputed start date is after a complete stop date, the start date will be set equal to the complete stop date.

Stop Dates:

1. If the year is unknown, then the date will not be imputed and will be assigned a missing value.
2. If the month is unknown, then 'December' will be assigned.
3. If the day is unknown, then the last day of the month will be assigned.

7.3 Protocol Deviations

Protocol deviations will be classified as major/minor by the MPBC protocol deviations review committee. The committee will determine the impact of the deviation on the study subjects' safety and rights, study compliance, data quality, and the proposed analyses. A subject level listing will report the description of the deviation and the impact.

A table of protocol deviations will summarize them by major/minor into the following categories:

- Informed Consent
- Inclusion/Exclusion
- Study Treatment
- Prohibited Concomitant Medication
- Trial Procedures
- Safety Reporting
- Discontinuation
- Miscellaneous

7.4 Baseline Values

Baseline values are from Baseline Visits for all measures, except C-SSRS, AUDIT, DUDIT, resting blood pressure (BP), Body Mass Index (BMI). For C-SSRS, the initial screening visit will be conducted with the ‘Lifetime’ version of the measure. The Independent Rater Screening assessment of ‘Since Last Visit’ suicidal ideation and behavior will be used as ‘Baseline.’ For the AUDIT and DUDIT measures and resting BP, BMI, results collected at Screening will be used as the Baseline value.

7.5 Participant Disposition and Dosing Summary

The All Enrolled Set will be used in the summary of participant disposition. The Safety Set will be included in the summary of accountability. The number and percent of participants who completed or discontinued the study will be displayed with reasons for early termination, where the percent is with respect to the total number of participants. The timepoint of doses and total MDMA (mg) administered will be summarized for the Safety Set.

7.6 Demographics and Baseline Characteristics

Participant demographic data and Baseline characteristics will be summarized descriptively for the Safety Set by treatment group and overall.

7.7 Efficacy Analyses

Due to the early termination of the study, the primary, secondary, and exploratory efficacy analyses specified in V1 of the SAP were removed. For all primary and secondary endpoints descriptive statistics (n, mean, standard deviation, median, interquartiles, range, or counts and percentages where appropriate) by timepoint will be provided for the overall sample and by treatment received.

7.7.1 Primary Effectiveness Analysis

Because of early termination at 1/3 of the planned sample size, the primary effectiveness analysis is no longer valid and will not be executed. Ninety-five percent confidence intervals will be calculated for the CAPS-5 raw means and change from baseline at T2 and T2.2 (for the 2 session group).

7.7.2 Secondary Effectiveness Analysis

The SDS will be presented in a similar manner to the CAPS-5 with descriptive statistics (n, mean, standard deviation, median, interquartile range, or counts and percentages where appropriate) by timepoint for the overall sample and by treatment received. Ninety-five percent confidence intervals will be calculated for the SDS raw means and change from baseline at T2 and T2.2 (for the 2 session group).

7.7.3 Exploratory Analyses

Data collected of the exploratory measures will be presented in by participant listings.

7.8 Safety Analyses

Safety analyses will confirm safety data with summary tables listing exposure to IMP, unsolicited AEs, concomitant medications, suicidal ideation and behavior, and vital signs overall and by treatment received. If a participant has more than one AE mapped to the same PT, that AE will be reported once using the highest severity. AEs that occur on Day 0 (Experimental Session), Day 1, Day 2 after IMP administration will be presented separately. Comparisons will be presented of relative incidence of AEs during experimental Sessions.

Frequency and incidence of concomitant medications will be displayed by generic name, sorted by class, and summarized overall and by treatment group. Frequency and incidence of positive or serious ideation and suicidal behavior will be presented using descriptive statistics of C-SSRS scores in tabular format. Vital signs (heart rate, blood pressure, and body temperature) for Experimental Sessions will be summarized using descriptive statistics in tabular format listing values at pre-IMP administration, prior to the supplemental dose, and at the end of each Experimental Session by treatment group.

7.8.1 Analysis of Exposure

The total mg exposure of participants will be summarized. Data will be tabulated for the Safety Set.

7.8.2 Analysis of Adverse Events

The primary measure of safety will be the reporting of unsolicited AEs. All AEs collected from Enrollment to Termination will be categorized as follows:

- Pretreatment AEs are defined as AEs that occur during the Preparatory Period prior to the first dose in the first Experimental Session
- Treatment Emergent AEs are defined as AEs that occur during the Treatment Period from the first Experimental Session to final study visit
- AEs that occur one and two days after MDMA administration
- AESIs are defined as AEs specified in the protocol related to cardiac function, serious suicidal ideation/behavior, and abuse liability
- Follow-up Period AEs are defined as AEs that occur during the Follow-up Period after the last Integrative Session through Termination
- AEs leading to discontinuation of IMP
- SAEs

Verbatim terms on case report forms will be mapped to preferred terms (PT) and system organ class (SOC) using the Medical Dictionary for Regulatory Activities (MedDRA) Version 24.0

Frequency and incidence of AEs will be displayed by PT, sorted by SOC, severity, and seriousness. AEs will be analyzed and presented as follows:

- If a participant has more than one AE mapped to the same PT, that AE will be reported once using the highest severity
- Relationship as determined by the Clinical Investigator
- AEs that occur on day of Experimental Sessions and two days after IMP administration will be presented separately.

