## **10.0 Safety**

### **10.1 Adverse Events**

In accordance with guidance for the specific study site, FDA Safety Reporting Requirements for INDs and BA/BE Studies, an Adverse Event (AE) is defined as any medical occurrence in a participant, including any abnormal sign (e.g., abnormal physical exam or laboratory finding), symptom, or disease, temporally associated with the participant’s involvement in the research, whether or not considered related to participation in the research. This definition includes concurrent illnesses or injuries and exacerbation of pre-existing conditions.

Events related to planned treatments or physician visits for Baseline conditions collected in the medical history will not be collected, unless there is an exacerbation of the condition, in which case they will be actively followed until resolution.

An unexpected AE is one that is not listed in the current IB or an event that is by nature more specific or more severe than a listed event.

The site physician will be responsible for reviewing and confirming all AEs and SAEs collected during the study. The therapy pairs will collect AEs during study visits from Enrollment (Visit 0) through Study Termination. Participants will be asked directly how they are feeling during each contact, and AEs may be captured spontaneously during therapy sessions, telephone calls, or other correspondence. Completed measures may create suspicion that an AE occurred; in this case, the site staff should follow-up with the participant.

All AEs will be monitored by the therapy pair until resolution or, if the AE becomes chronic, a cause can be identified. If an AE is unresolved when a participant terminates from the study, a clinical assessment will be made by the site physician, investigator, and/or Medical Monitor as to whether continued follow-up of the AE is warranted.

The severity of events reported on the “Adverse Events” eCRF will be determined by the site physician as:

- Mild: No limitation in normal daily activity
- Moderate: Some limitation in normal daily activity
- Severe: Unable to perform normal daily activity

The seriousness and relationship of study treatment to an AE will be determined by the Investigator based on the following definitions:

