### **13.2.4 Safety Analyses**

Safety analyses will confirm safety data with summary tables listing exposure to IMP, unsolicited AEs, concomitant medications, suicidal ideation and behavior, and vital signs overall and by group. If a participant has more than one AE mapped to the same PT, that AE will be reported once using the highest severity. AEs that occur on Day 0 (Experimental Session), Day 1, Day 2 after IMP administration will be presented separately. Assess relative incidence of AEs during Experimental Sessions such as clinical signs and symptoms, such as chest pain, shortness of breath, or neurological symptoms or any other signs or symptoms that may be indicative of a medical complication of the IMP.

Frequency and incidence of concomitant medications will be displayed by generic name, sorted by class, and summarized by treatment group, analysis set, and category. Concomitant medications taken on Day 0 (Experimental Session), Day 1, Day 2 after IMP administration will

be presented separately. Any psychiatric concomitant medications will be tabulated by period (Preparatory, Treatment Period, Follow-up Period). Frequency and incidence of positive or serious ideation and suicidal behavior will be presented using descriptive statistics of C-SSRS scores in tabular format. Vital signs (heart rate, blood pressure, and body temperature) for Experimental Sessions will be summarized using descriptive statistics in tabular format listing values at pre-IMP administration, prior to the supplemental dose, and at the end of each Experimental Session by treatment group. Additional details are available in the Statistical Analysis Plan.

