2.3 Safety Objectives

The overall safety objective is to assess severity, incidence and frequency of AEs, AEs of Special Interest (AESIs), and Serious Adverse Events (SAEs), concomitant medication use, and vital signs to support the package insert for MDMA-assisted therapy. The following safety objectives will evaluate the safety of MDMA-assisted therapy:

1. Assess incidence of AEs during Experimental Sessions that may be indicative of a medical complication of the Investigational Medicinal Product (IMP), such as clinical signs and symptoms of chest pain, shortness of breath, or neurological symptoms or any other signs or symptoms that prompt additional vital sign measurements.
2. Assess incidence of AEs by severity
3. Assess incidence of Treatment Emergent AEs (TEAEs) by severity.
4. Assess incidence of TEAEs by severity taken during an Experimental Session and through 2 days after IMP administration.
5. Assess incidence of AESIs, defined as AEs specified in the protocol related to cardiac function and abuse liability.

6. Assess incidence of AEs by severity categorized as leading to discontinuation of IMP, resulting in death or hospitalization, and continuing at Study Termination.
7. Assess incidence of SAEs.
8. Assess incidence of psychiatric concomitant medications taken during an Experimental Session and through 2 days after IMP administration.
9. Assess incidence of any psychiatric concomitant medications taken during the Treatment Period.
10. Assess incidence of serious suicidal ideation and positive suicidal behavior assessed with the Columbia Suicide Severity Rating Scale (C-SSRS).
11. Assess mean changes in blood pressure, heart rate, and body temperature from pre-IMP administration to end of each Experimental Session.

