7.8.5 Summary of Vital Signs

Vital signs (heart rate, BP, and body temperature) for Experimental Sessions will be summarized using descriptive statistics in tabular format listing values at pre-IMP, prior to the supplemental dose, and at the end of each Experimental Session.

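### SAP 7.8.2 lets an AE that starts before dosing and worsens afterwards be classed as pretreatment, and the SAP lists no output for AEs ongoing at Study Termination or for as-needed session vital signs

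*SAP*

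**What the plan says.** SAP 1.0 states that, after early termination at about 20 participants, the analyses are directed at safety only. SAP 8.0 places the final analysis after database lock.

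**Classification of AEs.** Under SAP 7.8.2, "All AEs collected from Enrollment to Termination will be categorized as follows". Two of the categories matter here. The first: "Pretreatment AEs are defined as AEs that occur during the Preparatory Period prior to the first dose in the first Experimental Session". The second: "Treatment Emergent AEs are defined as AEs that occur during the Treatment Period from the first Experimental Session to final study visit". A further rule in the same section reports a preferred term that recurs in one participant a single time, at its worst grade. It does not say whether this is done within each period or across the whole study. On collection, Protocol 10.1 says: "The therapy pairs will collect AEs during study visits from Enrollment (Visit 0) through Study Termination". Under Protocol 4.3, the taper of psychiatric medication falls before Visit 3, and so before the first dose.

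**Objective 6.** SAP 2.3 item 6 asks for AEs by severity that lead to IMP discontinuation, and for those "resulting in death or hospitalization, and continuing at Study Termination".

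**Objective 1.** SAP 2.3 item 1 asks for in-session AEs that may point to a medical complication, including "any other signs or symptoms that prompt additional vital sign measurements". The analysis text in Protocol 13.2.4 keeps that subset: "such as chest pain, shortness of breath, or neurological symptoms or any other signs or symptoms that may be indicative of a medical complication". SAP 7.8 keeps only the relative incidence of in-session AEs in general.

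**Vital signs.** SAP 7.8.5 provides descriptive statistics "listing values at pre-IMP, prior to the supplemental dose, and at the end of each Experimental Session". Footnote F to Protocol Tables 5 and 6 also allows readings as needed, and Protocol 9.2.2.1 calls for extra readings when symptoms such as chest pain or confusion arise.

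**The concern.** The definition of treatment-emergence carries most of the weight in a safety-only report. Here it turns on occurrence alone. Symptoms that appear while psychiatric medication is withdrawn are foreseeable, AE collection is already running at that time, and dosing follows shortly after Baseline. If such a symptom becomes worse after MDMA, the change belongs in the treatment-emergent tables, and the SAP has no rule that puts it there.

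The other gaps are of a different kind. Two stated safety objectives are not fully carried through to outputs. AEs that had not resolved when the participant left are not summarised, and the readings taken because something looked wrong during a session have no place in the tables.

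**Working it through.** There is no figure in the plan to reproduce. The check sets the objectives and definitions beside the listed outputs.

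**1. A worsening taper-phase AE.** Take, as an illustration only, a participant with mild insomnia from the taper that becomes severe after the first dose.

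| How the worsening is recorded | Highest-severity rule | Pretreatment table | TEAE table |
|---|---|---|---|
| One record, re-graded | either reading | severe | no entry |
| Two records | within period | mild | severe |
| Two records | once across the study | one severe entry, period not specified | same single entry |

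Only the second row gives the right answer. In the first, the onset date keeps a post-dose severe event in the pretreatment category. In the third, the outcome depends on a choice that the SAP does not make. The documents do not say which form of recording the eCRF uses. Protocol 10.1 counts an exacerbation of a pre-existing condition as an AE, which makes two records possible, but it does not say that a change in grade of an AE already open must be logged anew.

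The third row can also err the other way. If an AE is severe in the taper and recurs mildly after dosing, a study-wide highest grade could bring the severe grade into the TEAE table.

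**2. Objective 6 against SAP 7.8.2.** The objective has four parts:
- leading to IMP discontinuation: own category;
- resulting in death: reached through SAEs (Protocol 10.1.2);
- resulting in hospitalization: reached through SAEs (same section);
- ongoing at Study Termination: no output anywhere in SAP 7.8 to 7.8.5.

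The information should exist for the fourth part, because Protocol 10.1 requires a clinical assessment of any AE unresolved at termination.

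**3. Objective 1 against SAP 7.8.** In-session AEs are reported, and events on the session day and the two days after are displayed separately. The complication-type subset is neither defined nor flagged.

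**4. As-needed vital signs against SAP 7.8.5.** Protocol Table 9 schedules readings at 8:55, 10:30 and 16:30. The gap after the second is 16:30 − 10:30 = 6 hours, and it covers the time after the supplemental dose. Protocol 7.3.1 also makes the return of raised vital signs to pre-dose levels a condition for ending the session, so the last scheduled reading may lie close to the first. As-needed readings are the only ones provided for inside that gap, and no output includes them.

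**5. Size.** The documents give no event counts, so the frequency of misclassification cannot be estimated. The weight of one case can. Assuming that all of about 20 participants were dosed and that the 1:1 allocation gave about 10 per arm, one participant is 1/20 = 5 percentage points of a preferred term's incidence overall and 1/10 = 10 points in an arm. If fewer were dosed, each case weighs more.

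**The case against.** The best defence is that nothing is lost. SAP 7.8.2 categorises every AE from enrolment to termination, so a taper-phase AE appears at least as pretreatment. An exacerbation counts as an AE under Protocol 10.1, and if logged as new it is treatment-emergent. Serious suicidality is covered by the AESI category, and SAP 7.8.4 has a shift table for suicidal ideation. The vital-sign objective is item 11, mean change from pre-dose to session end, which the three timepoints serve. Protocol 13.2.4 names the same three.

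Much of this stands, and it rules out several stronger readings that a reader might draw:
- *Worsening taper-phase AEs go unreported.* Not supported. The risk is misclassification, and it is conditional on eCRF practice.
- *Deaths and hospitalizations are not covered.* Not supported. Both are SAE criteria, and SAEs have their own category.
- *In-session events such as chest pain would not be seen.* Not supported. They would appear in the session-day displays; only the flagged subset is missing.
- *The TEAE window has two conflicting ends.* The mention of the Treatment Period is loose, but the SAP names the final study visit as the end, and the protocol synopsis (Safety Objectives, item 3) runs to Study Termination. A separate Follow-up Period category means that no AE is lost on either reading. Day counts for the window would not measure any of the problems described here.
- *Every gap makes the treatment look safer.* Too strong. Missing subset tables do not remove AEs from the main displays, and a study-wide severity rule can also overstate TEAE severity.

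The defence does not supply a worsening rule, a scope for the highest-severity rule, or an output for unresolved AEs. The suicidality outputs do not cover other psychiatric symptoms such as anxiety or insomnia.

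**Conclusion.** The point holds in a limited form. Four things follow directly from the text: the TEAE definition has no worsening clause; the highest-severity rule is not tied to a period; AEs ongoing at Study Termination have no listed output although an objective asks for them; and the Objective 1 subset and as-needed session readings are not shown separately.

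The consequence for TEAE incidence or severity is conditional. It arises if the eCRF re-grades a single record, or if the severity rule is applied across the whole study. Its frequency is unknown; the 5- and 10-point figures are the effect of one such participant, under the assumptions stated above, and not an estimate of bias. The point does not undermine the safety report as a whole. It is worth settling before lock because safety is now the stated focus and the severity queries are easiest while the database is open.

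**What to change.** - In SAP 7.8.2, define a TEAE as an AE with onset, or increase in severity, on or after the first dose, through Study Termination. This matches the window in the protocol synopsis.
- State that the highest-severity rule applies within each period.
- Before lock, query the severity at first dose of each AE that was ongoing then.
- Add a table, by severity and arm, of AEs ongoing at Study Termination.
- Add a listing of unscheduled session vital signs beside the AEs recorded in the same session. This serves Objective 1 without needing the eCRF to link a reading to the AE that prompted it, a link that the documents do not describe.

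The cost is two sentences of SAP text, two small outputs for about 20 participants, and a few site queries. Some queries may need grading in retrospect; those grades should be marked as such.
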